6.4. Other Efficacy Endpoints Analysis

The other efficacy endpoints are as follows:

- Change from baseline in weekly average of the total daily (24-hour) use of albuterol/salbutamol inhalation aerosol (number of inhalations) at weeks 4, 8, and 12
- Change from baseline in percentage of rescue-free days (defined as 24-hour periods with no rescue medication usage) during the 12-week treatment period
- Change from baseline in percentage of symptom-free days (defined as 24-hour periods with asthma symptom score of 0) during the 12-week treatment period
- Change from baseline in percentage of asthma-control days (defined as 24-hour periods with asthma symptom score of 0 and no rescue medication usage) during the 12-week treatment period
- Change from baseline in 1-hour postdose percent predicted morning FEV₁ at week 1
- Change from baseline in weekly average of the daily evening PEF over the 12-week treatment period
- Change from baseline in weekly average of the percent predicted trough morning FEV₁ at weeks 1, 2, 4 and 8
- Proportion of patients who achieve at least a 15% increase in morning FEV₁ at 1-hour postdose at day 1 (the RV/TV1), week 1, and week 12

- Change from baseline in asthma control (measured by C-ACT) score at weeks 4, 8, and 12
- Time to consistent onset of effect defined as the decrease from baseline in daily rescue medication use on 3 consecutive days

6.4.1. Definition

6.4.1.1. Percentage of Rescue-free 24-Hour Periods

Rescue-free days are defined as 24-hour periods with no use of rescue medication. An entry in the electronic patient diary of zero inhalations will indicate a rescue-free 24-hour period. The percentage of rescue-free 24-hour periods is defined as the percentage of rescue-free days over the weekly analysis day during the treatment period. The entry on the day of the RV (TV1) excluding records prior to the first IMP dose is defined as day 1. A minimum of 60% of full days during the 12-week treatment period (or relative to the number of days that the patient participated in the study) cannot be missing in order for a patient to be included in this analysis.

6.4.1.2. Percentage of Symptom-free 24-Hour Periods

The asthma symptom scores are specified in Section 6.3.1.3. Scores of zero for both morning and evening indicate a 24-hour symptom-free period. The calculations of the percentage of symptom-free 24-hour periods will be based on the weekly analysis day data recorded during the treatment period. The missing data will be imputed according to the rules specified in Table 2. A minimum of 60% of full days during the 12-week treatment period (or relative to the number of days that the patient participated in the study) cannot be missing in order for a patient to be included in this analysis.

6.4.1.3. Percentage of Asthma-control 24-Hour Periods

An asthma-control 24-hour period is defined as a 24-hour period with asthma symptom scores of zero and no rescue medication use as recorded in the electronic patient diaries. The calculations of the percentage of asthma-control 24-hour periods will be based on the weekly analysis day data recorded during the treatment period. The missing data will be imputed according to the rules specified in Table 3. A minimum of 60% of full days during the 12-week treatment period (or relative to the number of days that the patient participated in the study) cannot be missing in order for a patient to be included in this analysis.

6.4.1.4. Weekly Average of the Daily Trough Evening PEF

A handheld spirometry device measuring FEV₁ and PEF will be provided to patients at the SV and used to determine the evening PEF throughout the course of the study.

Trough evening PEF will be determined in the evening before administration of IMP. Daily PEF time will be compared with IMP dose time. If a PEF measurement is performed after the IMP dose, a 10-minute window will be allowed and included in the analysis, otherwise the PEF measurement will be ignored.

The first day postrandomization consists of the electronic patient diary entry on the evening of the day of the RV (TV1). For the purpose of the efficacy analyses of weekly average of daily

evening PEF measurements, the values will be the averages based on the available data for that week. The averages will be calculated as the sum of evening PEF values divided by the number of nonmissing assessments. There will be no imputation applied to postrandomization assessments.

6.4.1.5. Time to Consistent Onset of Effect

Patients will record the number of inhalations of rescue medication (albuterol/salbutamol HFA MDI [90 mcg ex-actuator] or equivalent) each morning and evening in the electronic patient diary. Total daily use will be calculated after the RV. The time to consistent onset of effect is defined as a decrease from baseline in daily rescue medication use on 3 consecutive days.

6.4.2. Analysis Methods for Other Efficacy Variables

The analysis of the other efficacy variables will be performed on the ITT analysis set without retrieved dropout data.

6.4.2.1. Change from Baseline in the Weekly Average of the Total Daily (24-hour) use of Albuterol/Salbutamol Inhalation Aerosol (Number of Inhalations) at Weeks 4, 8, and 12

The change from baseline in weekly average of total daily (24-hour) use of albuterol/salbutamol inhalation aerosol (number of inhalations) at weeks 4, 8, and 12 will be analyzed using an MMRM with effects due to baseline value, sex, age, (pooled) investigational center, previous therapy (ICS or NCS), week, treatment, and week-by-treatment interaction. No explicit structure will be assumed for the covariance among the repeated measures. However, if there is a convergence problem with unstructured covariance, then a compound symmetry covariance structure will be assumed.

6.4.2.2. Change from Baseline in the Percentage of Rescue-free Days (Defined as 24-hour Periods with no Rescue Medication Usage) During the 12-week Treatment Period

The change from baseline in the percentage of rescue-free days (defined as 24-hour periods with no use of rescue medication recorded in the morning and evening) as recorded in the patient diaries during the 12-week treatment period will be summarized and compared between treatment groups using the Wilcoxon-Mann-Whitney test.

Example SAS code for this analysis:

```
proc npar1way data=salf wilcoxon;
  where treat in ("A", "D");
  class treat;
  var change;
  output out=yyy wilcoxon; run;
```

where: change is the change from baseline in percentage of rescue-free days. The code is executed for each pair of treatment comparisons of interest.

6.4.2.3. Change from Baseline in the Percentage of Symptom-free Days (Defined as 24-hour Periods with Asthma Symptom Score of 0) During the 12-week Treatment Period

The change from baseline in the percentage of symptom-free days (defined as 24-hour periods with asthma symptom scores of zero) as recorded in the patient diaries during the 12-week treatment period will be summarized and will be compared between treatment groups using the Wilcoxon-Mann-Whitney test.

6.4.2.4. Change from Baseline in the Percentage of Asthma-control Days (Defined as 24-hour Periods with Asthma Symptom Score of 0 and no Rescue Medication usage) During the 12-week Treatment Period

The change from baseline in the percentage of asthma-control days (defined as 24-hour periods with asthma symptom scores of zero and no rescue medication use) during the 12-week treatment period will be summarized and compared between treatment groups using the Wilcoxon-Mann-Whitney test.

6.4.2.5. Change from Baseline in 1-Hour Postdose Percent Predicted Morning FEV₁ at Week 1

On the morning of the week 1 visit (TV2), patients will perform their predose FEV₁ assessment at the investigational center. They will take their morning dose of the IMP, and subsequently perform the 1-hour postdose FEV₁ measurements using the handheld device. Patients, who have been withdrawn from IMP but remain in the study, will be asked to perform the 1-hour postdose lung function assessments at the visit although patients will not be taking a dose of IMP. The assessment should be performed approximately 1 hour after the predose lung function assessments were obtained.

The change from baseline in 1-hour postdose percent predicted morning FEV₁ at week 1 will be analyzed using an ANCOVA model with effects due to baseline percent predicted FEV₁, sex, age, (pooled) investigational center, previous therapy (ICS or NCS), and treatment. In cases where the 1-hour postdose value is missing at week 1, the 1-hour postdose at baseline (RV/TV1) will be used.

6.4.2.6. Change from Baseline in the Weekly Average of the Daily Evening PEF Over the 12-week Treatment Period

The analysis of change from baseline in weekly average of daily evening PEF over the 12-week treatment period will be performed using an MMRM with effects due to baseline weekly average of daily evening PEF, sex, age, (pooled) investigational center, previous therapy (ICS or NCS), week, treatment, and week-by-treatment interaction. No explicit structure will be assumed for the covariance among the repeated measures. However, if there is a convergence problem with unstructured covariance, a compound symmetry covariance structure will be assumed.

6.4.2.7. Change from Baseline in Weekly Average of the Percent Predicted Trough Morning FEV₁ at weeks 1, 2, 4 and 8

The change from baseline in weekly average of the percent predicted trough morning FEV₁ will be summarized descriptively by week and treatment.

6.4.2.8. Proportion of Patients who Achieve at Least a 15% increase in morning FEV₁ at 1-hour postdose at Day 1 (RV/TV1), Week 1, and Week 12

The proportion of patients who achieve at least a 15% increase in morning FEV₁ at 1-hour postdose at day 1 will be analyzed using a logistic regression model with effects due to previous therapy (ICS or NCS) and treatment. The proportion of patients who achieve at least a 12% increase in FEV₁ at 1-hour postdose at week 12 will be analyzed similarly.

6.4.2.9. Change from Baseline in Asthma Control (measure by C-ACT) score at Weeks 4, 8, and 12

The change from baseline in C-ACT score at weeks 4, 8 and 12 will be summarized descriptively by visit and treatment.

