A rescue-free day is defined as a 24-hour period with no use of rescue medication recorded. The baseline percentage of rescue-free days is defined as the percentage of rescue-free days over the 7 days prior to the RV. An entry of zero inhalations for both morning and evening will indicate a rescue-free 24-hour period.

Total Daily (24-Hour) Asthma Symptom Score:

The total daily asthma symptom score is defined as the average of the daytime and nighttime scores. The baseline total daily asthma symptom score is defined as the average of recorded (nonmissing) total daily asthma symptom scores over the 7 days prior to randomization. Five out of the last 7 nonmissing values are required for a patient to be randomized. If a minimum of

5 nonmissing values cannot be satisfied during the entire run-in period (14-30 days), the patient's asthma symptom score will include days beyond 7 days prior to the randomization or replaced by the overall asthma symptom score. No missing data imputation rule will apply.

Percentage of Symptom-free Days (24-Hour Periods):

Symptom-free days are defined as 24-hour periods with asthma symptom scores of zero recorded on the asthma symptom score electronic patient diary for both morning and evening entries. The baseline is defined as the percentage of symptom-free days over the 7 days prior to randomization.

A 24-hour symptom-free period is associated with a score of zero on the asthma symptom score diary for both morning and evening entries. Should either the morning or evening entry be missing and the other value is equal to zero, the available value will be weighted by half, and similarly the denominator will be modified to reflect the missing value. If both, morning and evening values, are missing for a particular day, the value will not be used in the calculation of percentage. [Table 2](#) illustrates a week of baseline symptom score and imputation rules as recorded in the electronic patient diary.

Table 2: An Example of Baseline Electronic Patient Diary Data for Symptom-free Days

Analysis Day	Morning score	Evening score	Value used for numerator of percentage calculation	Value used for denominator of percentage calculation
1	3	0	0	1
2	Missing	Missing	Not used in calculations	Not used in calculations
3	0	0	1	1
4	1	3	0	1
5	Missing	2	0	1/2
6	Missing	0	1/2	1/2
7	0	0	1	1
Week's total			2.5	5

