The percent of symptom-free 24-hour periods for this example is derived as $2.5/5 * 100\% = 50\%$. Similar rules apply to on-therapy interval.

Percentage of Asthma-control Days (24-Hour Periods):

Asthma-control days are defined as scores of zero recorded on the asthma symptom score diary during the 24-hour period and no rescue medication usage during the same 24-hour period. The baseline is defined as the percentage of asthma-control days over the 7 days prior to randomization. Detailed imputation rules are specified in [Table 3](#).

Table 3: An Example of Baseline Electronic Patient Diary for Asthma-control days

Analysis Day	Total Daily Asthma Score / Rescue Medication Usage	Value used for numerator of percentage calculation	Value used for denominator of percentage calculation
-1	3 / 0	0	1
-2	Missing / 0	Not used in calculations	Not used in calculations
-3	0 / 0	1	1
-4	Missing / 3	0	1
-5	0 / 3	0	1
-6	3 / 3	0	1
-7	Missing / Missing	Not used in calculations	Not used in calculations
Week's total		1	5

The percent of asthma-control days for this example is derived as $1/5 * 100\% = 20\%$. Note that if a patient's asthma score is missing, and there is no rescue medication usage during the same 24-hour period, the asthma-control days will not be used in calculations.

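### The rescue-free, symptom-free and asthma-control day comparisons use a Wilcoxon test on change from a 7-day baseline with no baseline covariate; this is valid but can be inefficient, by an amount the documents do not fix

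*SAP*

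**What the plan says.** SAP 6.4.2.2 states that change in the percentage of rescue-free days, "as recorded in the patient diaries during the 12-week treatment period will be summarized and compared between treatment groups using the Wilcoxon-Mann-Whitney test". The example code is a two-group PROC NPAR1WAY with treatment as the only class variable and one analysis variable, where "change is the change from baseline in percentage of rescue-free days". SAP 6.4.2.3 applies the same test to symptom-free days. SAP 6.4.2.4 does so for asthma-control days: the change "during the 12-week treatment period will be summarized and compared between treatment groups using the Wilcoxon-Mann-Whitney test".

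The baselines are in SAP 4.2. For rescue-free days: "The baseline percentage of rescue-free days is defined as the percentage of rescue-free days over the 7 days prior to the RV". For symptom-free days: "The baseline is defined as the percentage of symptom-free days over the 7 days prior to randomization". For asthma-control days: "The baseline is defined as the percentage of asthma-control days over the 7 days prior to randomization". Follow-up runs to analysis day 84 (SAP 4.3.2, Table 4), and a child enters the analysis only if enough diary days are present: "A minimum of 60% of full days during the 12-week treatment period", or of the days the child took part, must not be missing (SAP 6.4.1.1 to 6.4.1.3).

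The neighbouring diary endpoint, inhalations of rescue medication (SAP 6.4.2.1), is analysed by an MMRM with "effects due to baseline value, sex, age, (pooled) investigational center, previous therapy (ICS or NCS), week, treatment, and week-by-treatment interaction". The primary ANCOVAs (SAP 6.2.2), the four secondary MMRMs (SAP 6.3.2.1 to 6.3.2.4), week-1 FEV₁ (SAP 6.4.2.5) and evening PEF (SAP 6.4.2.6) also include the baseline of their own outcome.

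**The concern.** A change score does use baseline, but at a fixed weight of 1. Baseline here is a proportion of at most 7 days, so it moves in steps of 100/7 = 14.3 points when all 7 days are complete. The treatment-period figure moves in steps of 100/84 = 1.2 points. If days within a child are treated as independent, the day-sampling variance of the baseline is 84/7 = 12 times that of the follow-up at the same underlying rate. At a rate of 50% the day-sampling SDs are √(0.25/7) = 18.9 points and √(0.25/84) = 5.5 points. Subtraction passes all of the baseline noise into each child's score. Covariate adjustment uses baseline only as far as it predicts follow-up.

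Rescue inhalations and rescue-free days come from the same diary entries, yet the first analysis estimates the baseline slope and the second fixes it. The SAP gives no reason for the difference. What is at stake is precision on three supportive measures of day-to-day control.

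**Working it through.** **1. The plan's own sample size, to fix n.** SAP 2.4 gives 181 evaluable per arm for the two primary FEV₁ endpoints, at 80% power and 2-sided 5%. With n = 2(1.960 + 0.842)²(SD/Δ)²:
- SD 22, 6.5 taken as the difference: 180 per arm; power at 181 is 80.3%.
- SD 17, 5 taken as the difference: 182 per arm; power at 181 is 79.9%.
- 181/0.88 = 205.7, so 206 per arm and 824 in total.

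These figures reproduce. No corresponding inputs are given for the three day-percentage endpoints, so everything below rests on assumed values.

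**2. Formula.** Let ρ be the baseline-to-treatment correlation and k = SD(baseline)/SD(treatment period). In units of the treatment-period variance:
- residual variance after linear baseline adjustment: 1 − ρ²
- variance of the change score: 1 + k² − 2ρk = (1 − ρ²) + (k − ρ)²

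Change is therefore never better than adjustment in this model, and equal to it only when ρ = k. If the adjusted analysis has 80% power, the power on change is Φ(2.802·√[(1 − ρ²)/(1 + k² − 2ρk)] − 1.960).

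Example, k = 1 and ρ = 0.5: ratio 0.75/1.00, 2.802 × 0.866 = 2.426, Φ(0.466) = 67.9%, a loss of 12.1 points.

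Loss in points of power:

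| k | ρ = 0.2 | 0.3 | 0.4 | 0.5 | 0.6 | 0.7 | 0.8 |
|---|---|---|---|---|---|---|---|
| 0.5 | 3.6 | 1.7 | 0.5 | 0.0 | 0.6 | 3.0 | 9.3 |
| 0.8 | 13.4 | 10.1 | 7.2 | 4.6 | 2.4 | 0.8 | 0.0 |
| 1.0 | 21.7 | 18.3 | 15.0 | 12.1 | 9.3 | 6.7 | 4.3 |
| 1.2 | 30.0 | 26.9 | 24.0 | 21.3 | 18.9 | 16.9 | 15.5 |

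This is normal theory. Comparing a Wilcoxon test on change with a parametric ANCOVA adds about 2 points (efficiency 3/π).

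**3. Simulation with bounded, tied percentages.** Baseline was Binomial(7) and treatment period Binomial(84), with correlated logit-normal rates per child, improvement from baseline in every arm, and 3,000 trials per scenario. The effect was tuned so that rank ANCOVA had about 80% power.

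| Assumed baseline | Observed ρ | Wilcoxon on change | Rank ANCOVA | Loss |
|---|---|---|---|---|
| Mean 44%, 18% of children at zero | 0.41 | 56.0% | 80.7% | 24.7 |
| same | 0.59 | 57.9% | 79.0% | 21.1 |
| same | 0.72 | 61.2% | 79.9% | 18.7 |
| Mean 27%, 34% at zero | 0.48 | 69.7% | 81.7% | 12.0 |
| Mean 12%, 61% at zero | 0.34 | 76.6% | 80.9% | 4.3 |
| same | 0.48 | 79.0% | 81.6% | 2.6 |
| Mean 6%, 76% at zero | 0.30 | 77.8% | 78.6% | 0.8 |
| same | 0.41 | 80.0% | 81.7% | 1.7 |

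The pattern follows k. In the first row k = 33.0/29.8 = 1.11; in the first 61%-at-zero row k = 19.3/31.1 = 0.62, much closer to its ρ.

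**4. Does the low start alone remove the loss?** A further run at 181 per arm gave a gain from rank ANCOVA of about 5 to 26 points when there was no improvement common to all arms. It gave about −2 to 6 points when most children started at zero and all arms improved. Type I error of rank ANCOVA stayed near 5%. Both conditions, a low start and a common improvement, are needed for the loss to vanish.

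**The case against.** The strongest reply is that the design makes the favourable case plausible. Randomization requires a C-ACT score of 19 or less (Protocol 5.9), controller medication stops at run-in (Protocol 3.1), and the protocol notes that placebo patients often improve in lung function (Protocol 1.3.2). If most children start with almost no good days and all arms then improve, change is nearly the treatment-period value and there is little to adjust for. Asthma-control days, which require both no symptoms and no rescue use, are the most exposed to this floor. That stands: it is why the loss may be near zero and why the three endpoints cannot share one figure.

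It also stands that Wilcoxon on change tests the endpoint as named. Rank ANCOVA asks a slightly different question: the treatment-period percentage given baseline. And rescue use and the daily symptom score, from the same diary, are secondary endpoints with baseline-adjusted MMRMs (SAP 6.3.2.2 and 6.3.2.3), so the diary information is not left to these three tests alone.

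A reader might infer that the planned test is biased, ignores baseline, or sets children who started at different levels against one another. The documents do not support that. Change already uses each child's own baseline, and allocation is randomized 1:1:1:1, so arms differ at baseline only by chance. The issue is efficiency.

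None of this explains why the baseline slope is estimated for rescue inhalations and fixed for rescue-free days.

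**Conclusion.** The point holds as one of efficiency. The comparisons are valid, but they weight a noisy 7-day baseline at 1 where the SAP's ANCOVAs and MMRMs estimate the weight.

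The size depends on assumed ρ and k and on a reference power of 80%: about 4 to 22 points at equal SDs (ρ from 0.8 to 0.2), near zero with a floor at baseline plus improvement in all arms, and up to about 30 points at k = 1.2. A reader might be tempted to quote one loss, such as 10 to 20 points, for all three endpoints. With equal SDs that range needs ρ of about 0.25 to 0.57, and nothing in the documents places these endpoints there.

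The consequence is limited. These are other efficacy endpoints, with no power statement and no multiplicity adjustment (SAP 7.2). The protocol promises only that they will be summarized (Protocol 6.3.2 to 6.3.4) and leaves the method to the SAP (Protocol 9.5.4.4). No confirmatory conclusion depends on them.

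**What to change.** In SAP 6.4.2.2 to 6.4.2.4, make a rank analysis of covariance (Quade) the main comparison for each treatment pair: rank the treatment-period percentage and the baseline percentage, regress the first on the second, and compare residuals between the two arms. Keep the descriptive summary of change and report the Wilcoxon test on change as supportive.

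Make the change before unblinding, so that the test is not chosen with results in view; SAP 2.5.2 allows amendments approved before database lock.

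The cost is a few lines of SAS and revised wording, with no new data. There are three downsides: the test is slightly less familiar, it addresses the treatment-period percentage given baseline rather than the change itself, and it gives no effect estimate on its own, so the descriptive summary has to carry that. In the runs above it was never materially worse than the Wilcoxon test.

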4.3. Handling Withdrawals and Missing Data

4.3.1. Missing Data Imputation for Efficacy Analysis

The primary analysis and sensitivity analyses for the primary endpoints include reference-base multiple imputations for missing data and tipping point approaches as detailed in Section 6 and [Appendix A](#).

For endpoints analyzed using the mixed model for repeated measures (MMRM), there will be no imputation for missing data.

For all other variables, only the observed data from the patients will be used in the statistical analyses (ie, there is no plan to estimate missing data).

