                 details);

var trt &covlist wk1 - wk12;

mnar model( wk1 - wk12 / modelobs = (trt = "D"));

run;

```

where: the order of &covlist includes: sex, (pooled) investigational center, previous therapy, base, and age
Note: wk1 - wk12 is the AVAL raw data, change from baseline values should not be used in PROC MI procedure.

- The ANCOVA model will be fitted to the above dataset using the model described in Section 6.2.2.1. The difference will be estimated in adjusted LS means and p-value will be output for each dataset. An example SAS code to the following will be used:

```

proc mixed data=fev_model;
  where week = "week 12";

  class sex center therapy trt;

  model chg= base sex age therapy trt;

  lsmeans trt/diff=CONTROL("Placebo") cl alpha=0.05;

  ods output Estimates=Est LSMeans=lsmeans Diffs=Diffs;

run;

```

where: chg is the change from baseline percent predicted FEV1 value at week 12.

- The results from the ANCOVA model will be combined using the following code:

```

data diff2;
  set diff;

  comparison=trt||' vs '||left(_trt);

run;

proc sort data=diff2;
  by comparison;

```

```
run;
```

6. The SAS[®] procedure PROC MIANALYZE procedure will be used to generate the final LS means for the treatment groups, treatment difference as well as p-values associated with treatment differences. The 95% confidence intervals for the treatment differences will be also calculated. An example of the SAS code will be used:

```
proc mianalyze data=diff2;  
    by comparison;  
    modeleffects estimate;  
    stderr stderr;  
    ods output ParameterEstimates=mianalyzeparm;  
run;
```

Change from Baseline in 1-hour Postdose Percent Predicted Morning FEV₁ at Week 12:

The 1-hour postdose percent predicted morning FEV₁ measurement will be performed at the investigational center at the RV, TV2 (week 1), TV3 (week 2), TV4 (week 4), TV5 (week 8) and TV6 (week 12). The MI method will be applied similarly to impute the 1-hour postdose missing data that are caused by early dropouts from IMP without including retrieve dropout data. Steps 1 to 6 will be repeated similarly.

Sensitivity Analysis: Effectiveness with retrieved dropout data:

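### SAP 6.4.2.5 fills a missing week-1 1-hour FEV₁ with the day-1 postdose value, which contradicts the observed-data rule in SAP 4.3.1 and enters a first-dose measurement as a week-1 result

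*SAP*

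**What the plan says.** SAP 4.3.1 sets three rules for missing efficacy data. The primary endpoints get multiple imputation, endpoints analysed by MMRM get none, and the rest follow a third rule: "For all other variables, only the observed data from the patients will be used in the statistical analyses". A parenthesis adds that "there is no plan to estimate missing data". The section contains no exception clause.

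SAP 6.4 lists "Change from baseline in 1-hour postdose percent predicted morning FEV₁ at week 1" among the other efficacy endpoints. SAP 6.4.2.5 specifies the model: the change "at week 1 will be analyzed using an ANCOVA model with effects due to baseline percent predicted FEV₁, sex, age", pooled center, previous therapy and treatment. It then adds: "In cases where the 1-hour postdose value is missing at week 1, the 1-hour postdose at baseline (RV/TV1) will be used".

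Three further provisions matter:

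- SAP 6.4.2: "The analysis of the other efficacy variables will be performed on the ITT analysis set without retrieved dropout data".
- SAP 4.2: baseline for the 1-hour endpoint is the predose measurement at the center at RV/TV1.
- SAP 4.3.2: assessments from an unscheduled early termination visit are moved to the next scheduled visit.

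**The concern.** The two SAP sections give opposite instructions for the same missing value, and the SAP gives no reason for the fill. SAP Section 11, which records departures from the protocol, does not mention it either.

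The fill is also weak in itself. The day-1 value belongs to a different time point and follows a single dose. The model then treats it as a real week-1 observation, so the estimate blends day-1 and week-1 responses and its standard error takes no account of the filling. At stake is how far the week-1 result can be read as a week-1 result. No primary or secondary conclusion depends on it.

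**Working it through.** The plan states no figure for this point, so the check is mainly textual.

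**Which missing-data rule applies?** The endpoint is not primary (SAP 6.4) and is analysed by ANCOVA, not MMRM (SAP 6.4.2.5). The third rule in 4.3.1 therefore covers it, and a missing value should stay missing. SAP 6.4.2.5 fills it.

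**What does the filled value contain?** Baseline is the predose RV/TV1 value, so the 1-hour RV/TV1 value gives a change that is generally not zero. Protocol Appendix B has the first dose observed at that visit, with the 1-hour test afterwards. The sponsor's own rationale (Protocol 9.5.4.1, SAP 6.2) places FEV₁ improvement on inhaled steroid as early as one week, and improvement on steroid with a long-acting beta-agonist on the same day. A day-1 value can therefore hold a salmeterol response, but little or none of the steroid effect that may be present at week 1.

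**Who is affected?**

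- Children on treatment whose week-1 test was missed or excluded. SAP 4.1 treats percent predicted values of 200% or more as missing in all analyses.
- Children who stopped IMP before TV2 and for whom the 4.3.2 mapping supplies no value. SAP 6.4.2.5 asks withdrawn children to be measured at TV2 without a dose, but 6.4.2 excludes retrieved dropout data.

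**Which way does the fill push?**

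| Child | Day-1 value compared with week 1 |
|---|---|
| FS, on treatment | contains salmeterol response, omits steroid effect gained by week 1 |
| FS, stopped, no mapped value | carries forward a salmeterol response after the drug was stopped |
| Fp, on treatment | omits steroid effect gained by week 1 |
| Fp, stopped, no mapped value | little drug response to carry forward |

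**How large could it be?** Shift in an arm mean = m × d, where m is the share of the arm filled and d is the gap between the day-1 value and the true week-1 value. The documents give neither, so both are assumed, with 206 patients per arm:

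- m = 1% (about 2 patients), d = 2 points: 0.01 × 2 = 0.02 points.
- m = 2% (about 4 patients), d = 6.5 points: 0.02 × 6.5 = 0.13 points.
- m = 10% (about 21 patients), d = 10 points: 0.10 × 10 = 1.0 point.

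The shift in a treatment difference is m₁d₁ − m₂d₂. It is zero if share and gap match between arms. In the extreme case of 1.0 point in opposite directions it reaches 2.0 points.

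For scale, take the blinded week-12 SD of 22 (Protocol 9.1) as the week-1 SD, which is an assumption. The standard error of a two-arm difference is then 22 × √(2/206) = 2.17 points. A shift of 0.13 is 0.13/2.17 = 0.06 of a standard error, and 1.0 is 0.46.

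**The case against.** The strongest reply is that a specific rule overrides a general one. Protocol 9.3 expects imputation rules suited to each endpoint, and Protocol 9.5.4.4 leaves the methods for these endpoints to the SAP. The SAP has other local rules: item means for the C-ACT (6.3.1.4) and the conventions for incomplete diary days (Tables 2 and 3). A programmer would follow 6.4.2.5. This stands as an account of what would be run. It does not remove the conflict with 4.3.1 or justify using a first-dose value at week 1.

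A reader might infer that the rule credits early discontinuers in general with a drug response. The documents do not support that. Protocol Table 3 schedules a 1-hour FEV₁ at the IMP discontinuation visit, and SAP 4.3.2 moves early termination assessments to the next scheduled visit, so many such children may already have a week-1 value. The SAP does not say whether the mapping or the fill comes first. The credit argument fits salmeterol in the FS arm. It does not fit the Fp arms, where a day-1 value comes before most or all of the steroid effect.

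A reader might also infer that week 1 and week 12 rest on opposite assumptions. In the Fp arms, a value taken before steroid effect is not far from a placebo-like value. Week 12 is not wholly placebo-based either: completers with implausible values are imputed from their own arm (SAP 6.2.2.2 and Appendix A).

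**Conclusion.** The contradiction between SAP 4.3.1 and 6.4.2.5 is literal, and the fill enters a day-1 measurement as an observed week-1 result. That much rests on the text alone.

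No firm size can be given. It is tempting to multiply 2% to 5% missing by a 5-point steroid effect and report 0.1 to 0.25 points. Both inputs would be assumptions, and the product describes one arm's mean, not a treatment difference. The direction is also open, because the fill can raise the value for some FS children and lower it for on-treatment Fp children. The effect is probably small if few tests are missing one week after randomization, which is itself an assumption.

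The endpoint is outside multiplicity control (SAP 7.2), and the week-12 primary analyses use their own imputation. This is a minor correction, worth making before database lock.

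**What to change.** Delete the substitution sentence from SAP 6.4.2.5 and analyse observed on-treatment week-1 data with the ANCOVA already stated, as 4.3.1 requires. Add a clause saying whether a value mapped under 4.3.2 counts as observed for this endpoint. The cost is one or two sentences and a few fewer patients in this one analysis.

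If the sponsor prefers to keep all randomized patients, the Appendix A imputation could supply week 1, since it covers the 1-hour series from that visit on: "The MI method will be applied similarly to impute the 1-hour postdose missing data that are caused by early dropouts from IMP". That also departs from 4.3.1, so it should be named there as an exception and the results pooled with PROC MIANALYZE. It is more work than the deletion.
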